4.1. Inclusion Criteria

Patient eligibility should be reviewed and documented by an appropriately qualified member of the investigator's study team before patients are included in the study.

Patients must meet all of the following inclusion criteria to be eligible for enrollment into the study:

1. Cytogenetic or PCR-based diagnosis of Ph+ CML or BCR-ABL1+ if Ph- (from initial diagnosis). NOTE: Ph- CML patients will not count towards the 150 patients for primary and secondary analyses, which include Ph+ CML patients only.

NOTE: All patients must have screening bone marrow (BM) cytogenetic analysis with conventional G banding performed within 30 days prior to study entry (unless CML disease status is proven to be MMR by quantitative reverse transcription polymerase chain reaction [qRT-PCR]). Examination of at least 20 metaphases is required.

2. Prior treatment with 1 or more TKIs for CML.
3. Any CML phase, as long as the patient is resistant to, intolerant of, or otherwise not appropriate for treatment with imatinib, dasatinib and/or nilotinib.

4. Eastern Cooperative Oncology Group (ECOG) Performance Status of 0 or 1 for CP patients, or 0, 1, 2, or 3 for 4th line CP (and beyond) and AP/ BP patients.
5. Adequate bone marrow function:
 - For 2nd and 3rd line CP CML patients:
 - Absolute neutrophil count $>1000/\text{mm}^3$ ($>1 \times 10^9/\text{L}$).
 - Platelets $\geq 75,000/\text{mm}^3$ ($\geq 75 \times 10^9/\text{L}$) absent any platelet transfusions during the preceding 14 days.
 - For 4th line CP and AP/BP CML patients:
 - Absolute neutrophil count $>500/\text{mm}^3$ ($>0.5 \times 10^9/\text{L}$).
 - Platelets $\geq 50,000/\text{mm}^3$ ($\geq 50 \times 10^9/\text{L}$) absent any platelet transfusions during the preceding 14 days.
6. Adequate hepatic and renal function:
 - AST/ALT $\leq 2.5 \times$ the upper limit of normal (ULN) or ALT/AST $\leq 5 \times$ ULN if attributable to liver involvement of leukemia.
 - Total bilirubin $\leq 1.5 \times$ ULN (unless the bilirubin is principally unconjugated and there is a strong suspicion of subclinical hemolysis (e.g. chronic hemolysis without clinical symptoms), or the patient has documented Gilbert's Disease);
 - Alkaline phosphatase $\leq 2.5 \times$ ULN.
 - Creatinine $\leq 1.5 \times$ ULN or estimated creatinine clearance (CrCL) $\geq 60 \text{ mL/min}$ as calculated using the standard method for the institution.
7. Able to take daily oral tablets.
8. Age ≥ 18 years.

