- Echocardiogram (ECHO) or multiple gated acquisition (MUGA) scan; Standard of care echocardiogram (ECHO) or multi-gated acquisition (MUGA) scan results may be used for screening if not longer than 12 weeks prior to the first bosutinib dose in the absence of past medical history of cardiovascular disease and presence of normal left ventricular ejection fraction (LVEF). If the patient has past medical history of cardiovascular disease or ongoing cardiovascular co-morbidities, ECHO or MUGA should be obtained within 7 days prior to the first bosutinib dose. Screening, unplanned, and End of Treatment assessments should be performed with the same test, ECHO or MUGA scan.
- Chest X-ray; Standard of Care chest X-ray results may be used for screening if not longer than 12 weeks prior to the first bosutinib dose in the absence of past medical history of pulmonary disease. If the patient has past medical history of pulmonary disease or ongoing pulmonary co-morbidities, then chest X-ray should be obtained within 7 days prior to the first bosutinib dose;
- Bone marrow aspirate sample for G-banding analysis (karyotype) and morphological assessment (% of bone marrow differential) is required at screening, unless the CML disease status is proven to be MMR by qRT-PCR. Conventional cytogenetic assessment will be done locally. If a bone marrow aspirate that meets all study requirements was obtained within 30 days prior to screening, these data may be used to replace the need for a bone marrow aspirate during screening. In Ph- CML patients, conventional cytogenetic assessments (to detect other potential cytogenetic abnormalities) and molecular cytogenetic assessments using FISH (to detect cryptic/variant translocations) are required at screening;
- qRT-PCR for molecular response assessment (BCR-ABL fusion transcript levels) and mutational analysis of the BCR-ABL kinase domain will be performed by a central laboratory. For CP CML, the assessments will be performed using peripheral blood sample. For Advanced Phase (AP and BP) CML, the assessments will be performed using peripheral blood and/or bone marrow samples; mutational analysis will be performed from the peripheral blood or bone marrow samples that were used for molecular response assessment;

- Hematology panel ([Appendix 9](#));

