9.2.1. Analysis of Primary Endpoint

The primary efficacy analyses are the percentage of cumulative confirmed MCyR in CP 2nd and 3rd line patients, cumulative confirmed MCyR in 4th and later line patients and the cumulative confirmed OHR in AP and BP patients by 1 year of bosutinib treatment (Week 52) assessed from the local laboratory data. The primary analyses will be the percentage of cumulative confirmed MCyR (for CP Ph+ CML patients) and cumulative confirmed OHR

(for AP and BP Ph+ CML patients) by 1 year of bosutinib treatment (week 52). Confirmed MCyR will be defined as (1) the attainment of confirmed MCyR (CCyR or PCyR) by 1 year for patients entering the study without CCyR achieved on the previous TKI therapy or (2) the maintenance of confirmed CCyR (achieved under the previous TKI therapy) for at least 1 year after starting treatment with bosutinib or (3) at least MMR by 1 year and a deeper molecular response compared to baseline. Patients with baseline PCyR that do not achieve CCyR are included in the analysis but they would be counted as non-responders. Initial cytogenetic (in the absence of MMR) and hematologic responses must be confirmed by 2 consecutive assessments at least 28 days apart.

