5.4. Other Analysis Sets

The evaluable analysis set are those treated patients with a valid baseline efficacy assessment for the respective endpoint (ie, [1] at least 20 metaphases from the baseline bone marrow cytogenetic assessment or a CCyR with at least 200 cells analyzed from the fluorescence in situ hybridization [FISH] baseline assessment or MMR from the baseline molecular assessment for cytogenetic endpoints or [2] a valid baseline hematologic assessment for hematologic endpoints as defined in [Appendix 1](#) or [3] a valid baseline molecular assessment from the central laboratory for molecular endpoints).

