6. ENDPOINTS AND COVARIATES

In general, the baseline value will be defined as the last non-missing value prior to first dose, unless specifically stated otherwise. Assessments performed on Week 1 day 1 will be assumed to be pre-dose per the schedule of activities in the Protocol.

An on-treatment evaluation is defined as any evaluation done during bosutinib therapy or within 28 days of last dose.

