7. HANDLING OF MISSING VALUES

In general, no imputation such as last observation carried forward (LOCF) will be used. For the time-to-event endpoints, such as time to response, DOR, time to transformation, PFS, and OS, the primary missing data handling method will be censoring as described in [Section 6.1](#).

In compliance with Pfizer standards for handling partial dates, if the month and year are present but day is missing, start date is set to 1st of month, and stop date is set to last day of month. If year is present but day and month are missing, start date is set to January 1st, and stop date is set to December 31st.

If there are missing items for the PRO endpoints, subscale scores can be prorated. This is done by multiplying the sum of subscale by the number of items in the subscale, then dividing by the number of items actually answered. This can be done on the scoring guide or by using the formula below:

Prorated subscale score = [Sum of item scores] x [N of items in subscale] \div [N of items answered]

When there are missing data, prorating by subscale in this way is acceptable as long as more than 50% of the items were answered (eg, a minimum of 4 of 7 items, 4 of 6 items, etc). The total score is then calculated as the sum of the unweighted subscale scores. The FACT scale is considered to be an acceptable indicator of patient quality of life as long as overall item response rate is greater than 80% (eg, at least 22 of 27 FACT-G items completed). This is not to be confused with individual subscale item response rate, which allows a subscale score to be prorated for missing items if greater than 50% of items are answered.

Handling of missing/incomplete patient central molecular data will be done by the following procedure: for post-baseline visits, assessments at a specific visit without a minimum number of ABL transcripts specified by the central laboratory will be not used for analysis.

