Handling of missing/incomplete patient local cytogenetic data will be done by the following procedure: for baseline visits, only bone marrow information with ≥ 20 metaphases will be used, otherwise the baseline response will be set to missing. For post-baseline visits, bone marrow information with 20 to 99 metaphases will be used over FISH information with at least 200 nuclei at a specific visit. FISH will only be used to assess CCyR. No conventional bone marrow cytogenetic assessment will be derived when ≥ 100 cells are reported as analyzed for Philadelphia chromosome as this will be considered an error in data entry. If on-treatment molecular monitoring is performed in lieu of conventional cytogenetics or FISH, CCyR may be imputed on a specific date if a MMR is achieved on that date. The results of conventional cytogenetic testing, FISH with ≥ 200 nuclei or banding with ≥ 20 metaphases, will be used in preference to molecular testing, provided they are available and performed on the same date.

Handling of missing/mismatched patient hematologic efficacy data will be done using the following procedure: for each patient, the observations will be sorted by visit and the relative day to first dose.

First, for each observation, peripheral blood and/or bone marrow differentials should add up to 100%. Some sites may not record 0% to reflect uncounted cell types as instructed. Instead, the corresponding field may appear as missing or “ND” even though data collection procedures have been vigorously followed. Also, the differentials may not exactly add up to 100%. To correct this problem, each domain of the differentials will be summed together. If the total is between 98.5% and 101%, the missing values are assigned 0%. Otherwise, the observation is left as is and the record is also to be reported as a data issue.

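### SAP Section 7 sets the baseline cytogenetic response to missing for patients whom SAP Section 5.4 admits on baseline MMR or FISH, so those who hold for 52 weeks without deepening fall to non-responder

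*SAP*

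**What the plan says.** **Who is evaluable.** SAP 5.4 accepts three kinds of baseline for cytogenetic endpoints: marrow with at least 20 metaphases, a FISH CCyR with at least 200 cells, "or MMR from the baseline molecular assessment for cytogenetic endpoints".

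**How baseline is derived.** The local cytogenetic paragraph of SAP 7 uses only baseline marrow with at least 20 "metaphases will be used, otherwise the baseline response will be set to missing". The same paragraph lets MMR stand in for CCyR, but only after treatment starts: "If on-treatment molecular monitoring is performed in lieu of conventional cytogenetics or FISH, CCyR may be imputed on a specific date".

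**Why patients without baseline metaphases will exist.** Protocol 6.1 says a marrow aspirate "is required at screening, unless the CML disease status is proven to be MMR by qRT-PCR". The note to the first inclusion criterion in Protocol 4.1 has the same exception: "unless CML disease status is proven to be MMR by quantitative reverse transcription polymerase chain reaction".

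**What counts as response.** Protocol 9.2.1 has three routes: a new confirmed MCyR in patients who enter without CCyR from the previous TKI; "the maintenance of confirmed CCyR (achieved under the previous TKI therapy) for at least 1 year after starting treatment with bosutinib"; or at least MMR by one year with a deeper molecular response than at baseline. SAP 6.1 requires the baseline cytogenetic response to be maintained for at least 52 weeks or improved upon, and keeps the deeper-molecular-response route. SAP 8.2.1 analyses the evaluable set and treats anyone without a demonstrated response by Week 52 as a non-responder.

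**The concern.** Section 5.4 treats baseline MMR as a valid cytogenetic baseline, and Section 7 discards it. The same MMR result can be read as CCyR after the first dose but is missing before it.

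The patients concerned are evaluable, in chronic phase, with an MMR baseline (or, rarely, a FISH one) and no usable marrow, who hold their response for a year without reaching a deeper molecular level. They stay in the denominator of the primary MCyR rate but cannot pass the maintenance-or-improvement test, because there is no baseline response to maintain or improve on. The protocol would count them as responders.

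The secondary cumulative MCyR rests on a similar maintenance-or-improvement test. The supportive MCyR and CCyR analyses in SAP 8.2.2 that leave out baseline responders could wrongly keep these patients in. The study tests no hypothesis (SAP 4.1), so what is at stake is bias in an estimate. Estimates are, however, the main efficacy output of this post-authorization commitment.

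**Working it through.** **1. Does any other rule supply the missing baseline?**

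- SAP 6 gives a general rule: "the baseline value will be defined as the last non-missing value prior to first dose, unless specifically stated otherwise". Section 7 states otherwise for baseline cytogenetics, so the general rule gives way.
- The molecular-data paragraph of SAP 7 covers later visits only: "for post-baseline visits, assessments at a specific visit without a minimum number of ABL transcripts specified by the central laboratory will be not used".
- The SAP Appendix 2 footnote allows CCyR by FISH in general, but Section 7 restricts the baseline to marrow.
- The deeper-molecular-response route in SAP 6.1 helps only patients who deepen. A patient who enters at MR4.5 has no deeper category to reach in the SAP's hierarchy.

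None of these closes the gap.

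**2. Classification under the literal text.** The last column takes the baseline MMR or FISH CCyR as baseline CCyR.

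| Held 52 weeks | Deepened | Baseline missing (SAP 7) | Baseline CCyR carried through |
|---|---|---|---|
| Yes | Yes | Responder | Responder |
| Yes | No | **Non-responder** | **Responder** |
| No | Yes | Responder | Responder |
| No | No | Non-responder | Non-responder |

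Only the second row changes.

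**3. The plan's own precision figure.** Protocol 9.1 gives a maximum standard deviation of 0.075 for 45 patients. √(0.25/45) = 0.0745, so it reproduces. It serves below as a yardstick.

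**4. Size of the error.** Let n be the evaluable patients in a primary CP cohort and h those in the second row. The literal rule lowers the rate by h/n. The values of h are assumed. The 45 (Protocol 9.1) and 106 (SAP 2) include AP and BP patients, so the CP denominators may be smaller; 35 is an assumed example.

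| n | h | Error (percentage points) |
|---|---|---|
| 45 | 1, 2, 3 | −2.2, −4.4, −6.7 |
| 106 | 2, 4, 6 | −1.9, −3.8, −5.7 |
| 35 | 2 | −5.7 |

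**5. Worked example (all counts assumed).** n = 45, of whom 4 have an MMR or FISH baseline, no usable marrow and no deepening. Two of the 4 hold for 52 weeks, and 21 of the other 41 respond. Intervals are exact 95% (Clopper-Pearson), as SAP 8.1.3 specifies.

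- Protocol rule: (21 + 2)/45 = 51.1% (35.8 to 66.3).
- Literal SAP: 21/45 = 46.7% (31.7 to 62.1).
- Difference: 2/45 = 4.4 points, and 0.0444/0.0745 = 0.6 of the maximum standard deviation.

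If a missing baseline were instead read as no baseline CCyR, the 2 who do not hold could be credited as new responders on two assessments 28 days apart. The rate could then reach (23 + 2)/45 = 55.6%, an error of at most +4.4 points.

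**The case against.** The strongest reply is that the SAP never says how a missing baseline enters the responder test. SAP 6.1 also describes cumulative response as any on-treatment response through Week 52. A patient who stays in MMR can have CCyR imputed at each visit, so a programmer might count that patient as a responder. On this view the outcome is undefined, and the direction of bias with it. Section 5.4 can also be read as implying that the assessment which admits a patient serves as that patient's baseline, with the Section 7 sentence aimed only at marrow samples with too few metaphases.

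Part of this stands. A programmer could depart from the literal text. But SAP 6.1 makes maintenance or improvement a condition of response, and neither can be shown against a missing baseline; non-responder is what the text gives. The lenient reading needs the added assumption that missing means no response, and it conflicts with the first route in Protocol 9.2.1, which is confined to patients entering without CCyR from the previous TKI. Dropping these patients would contradict Section 5.4. Reading Section 5.4 as the baseline rule gives the sensible result, but it has to override an explicit sentence in Section 7.

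The points on size also stand. The group is narrow: some patients in MMR will have a standard-of-care marrow that can be used, and those who deepen are already counted. The number affected is not in the documents. In SAP 8.2.2 only the MCyR and CCyR exclusions are exposed, since the molecular ones do not depend on the cytogenetic baseline.

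**Conclusion.** The concern holds. As written, SAP 7 does not carry through the baseline definition in SAP 5.4, and it misclassifies one identifiable group: chronic-phase patients evaluable on MMR, or rarely FISH, who hold for 52 weeks without deepening. The literal rule understates the primary MCyR rate by h/n. Each such patient costs 2.2 points at n = 45 and 0.9 points at n = 106 (1/106). The error is systematic, so the exact confidence interval will not reveal it.

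The direction rests on reading SAP 6.1 with 8.2.1 literally; the less supported reading errs upward. The actual size cannot be computed from the documents. This should be fixed, but it does not threaten a test decision, because there is none.

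**What to change.** Replace the baseline sentence in SAP 7 with the Section 5.4 criteria in order:

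1. Marrow with at least 20 metaphases.
2. If none, FISH CCyR with at least 200 cells.
3. If neither, CCyR imputed from MMR on the baseline molecular assessment.
4. Missing only if none of these is available.

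State that patients classified under steps 2 and 3 are judged by the 52-week maintenance rule or the deeper-molecular-response route, and that they count as baseline responders in the supportive MCyR and CCyR analyses of SAP 8.2.2. Report, for each primary CP cohort, how many patients have an MMR-based or FISH-based baseline.

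SAP 8.2.2 says all patients had reached Week 52 before 11 March 2020, so the primary analysis may already have been run. If so, check which rule was programmed and report the effect of any change.

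The cost is one or two sentences and one count per cohort, with no new data. The standard is not loosened: patients who neither hold for 52 weeks nor deepen remain non-responders.

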6.2. Study Period

The following procedures will be performed on treatment. Patients must be registered to the study after eligibility is confirmed within 3 days prior to receiving first dose of bosutinib.

Week 1 (Day 1, pre-dose and Day 7), Week 2, Week 3, Week 4 and Week 8 (± 1 day) on Day 7

- Hematology panel ([Appendix 9](#)); complete hematological assessment response;
- Liver function tests ([Appendix 9](#));
- Chemistry panel; including HbA1C, cholesterol, HDL, LDL, potassium, and magnesium, if clinically indicated ([Appendix 9](#));
- Coagulation tests ([Appendix 9](#));

- Urine or serum pregnancy test (for women of childbearing potential) (pre-dose Week1 Day 1 only) ([Appendix 9](#));
- Contraceptive check: patients of child-bearing potential will be required to affirm their use of 2 highly effective methods of contraception which will be documented in the patient's source document;
- Extramedullary disease assessment, if clinically indicated. Sites of extramedullary disease identified at screening should be followed during the course of treatment. Patients should be evaluated upon suspicion of new extramedullary disease;
- Hepatitis B serology testing, as clinically indicated;
- Patient diary card review ([Appendix 6](#));
- Bosutinib dispensation on Day 1.

Week 13, Week 26, Week 39, Week 52 (± 7 days), Week 78, Week 104, Week 130, Week 156, and Week 182 (± 21 days)

- Complete physical examination to include vital signs (sitting or supine blood pressure, heart rate and weight);
- Current smoking status.
- Extramedullary disease assessment, if clinically indicated. Sites of extramedullary disease identified at screening should be followed during the course of treatment. Patients should be evaluated upon suspicion of new extramedullary disease;
- Hepatitis B serology testing, as clinically indicated;
- ECG assessment, if clinically indicated;
- ECHO or MUGA scan assessment, if clinically indicated;
- Chest X-ray, if clinically indicated;
- ECOG Performance Status ([Appendix 8](#));

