7.1.1.2. Hematologic Response Assessment

Complete blood counts and differentials and extramedullary disease assessment (liver and spleen assessment) from the physical examination and bone marrow differentials will be used to determine response to treatment.

Hematologic responses must be of at least 4 weeks duration confirmed by 2 assessments at least 4 weeks apart. Complete hematologic response (CHR) and OHR (defined as CHR or RCP) will be evaluated by peripheral blood, and bone marrow differential (to define RCP) when available, only utilizing local laboratory results. Loss of hematologic response must be confirmed by 2 assessments at least 2 weeks apart. Note: if confirmation is lacking and the patient goes off treatment due to progressive disease, the assumption is that loss of hematologic response is confirmed for this study; therefore, the confirmation of loss of hematologic response 2 weeks apart is not required in this clinical context.

The definition of CHR for CP CML is outlined in [Appendix 11](#).

CHR for AP and BP CML is defined as white blood cell (WBC) count less than or equal to the institutional upper limit of normal (ULN); absolute neutrophil count (ANC) $1.0 \times 10^9/L$ or higher, platelet count $100 \times 10^9/L$ or higher; marrow blasts 5% or less with no peripheral blasts or promyelocytes; peripheral myelocytes + metamyelocytes less than 5%; basophils in peripheral blood less than 5%; and no evidence of extramedullary involvement.

Note: If an on-treatment CBC is scheduled within 1 week from the last platelet transfusion, it should be considered “Not Evaluable” for hematological response assessment, and a CBC should be repeated at least 1 week from the last platelet transfusion received.

Note: If an on treatment CBC is scheduled within 1 week from the last dose of G-CSF or GM-CSF growth factor, it should be considered “Not Evaluable” for response assessment and CBC should be repeated at least 1 week from the last dose of growth factor.

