Appendix 11. European LeukemiaNet Guidelines for Response in CML

Definitions of Hematologic, Cytogenetic, and Molecular Response²⁶

Response by Type	Definitions
Hematologic Complete (CHR)	WBC <10 x 10 ⁹ /L Peripheral Blood Basophils <5% No Peripheral Blood myelocytes, promyelocytes, myeloblasts in the differential Platelet count <450 x 10 ⁹ /L Spleen nonpalpable
Cytogenetic * Complete (CCyR) Partial (PCyR) Minor (mCyR) Minimal (minCyR) None (noCyR)	No Ph+ metaphases 1% to 35% Ph+ metaphases 36% to 65% Ph+ metaphases 66% to 95% Ph+ metaphases >95% Ph+ metaphases
Molecular Deep Molecular Response (MR4, MR4.5)	MR4= either (i) detectable disease with <0.01% BCR-ABL1 ^{IS} or (ii) undetectable disease in cDNA with >10 000 ABL1 transcripts MR4.5 =either (i) detectable disease with < 0.0032% BCR-ABL1 ^{IS} or (ii) undetectable disease in cDNA with >32,000 ABL1 transcripts in the same volume of cDNA used to test for BCR-ABL1.
Major (MMR)	Ratio of BCR-ABL ^{IS} ≤0.1%**.

Abbreviations: CHR, complete hematologic response; CCyR, complete cytogenetic response, PCyR, partial cytogenetic response; Ph+, Philadelphia Chromosome positive; MCyR, major cytogenetic response; mCyR, minor cytogenetic response; minCyR, minimal cytogenetic response; noCyR, no cytogenetic response; MR4, MR4.5, deep molecular response; MMR, major molecular response;.

*If bone marrow metaphases cannot be obtained or evaluated by chromosome banding analysis, the definition of CCyR (defined as <1% for FISH) may be based on interphase FISH of blood cells, provided that it is performed with Dual-Color Dual-Fusion or Dual-Fusion FISH probes and at least 200 nuclei are scored. PCyR and CCyR are counted together and reported as MCyR.

**With >=5,000 ABL1 transcripts.

Definitions of Hematologic Response for AP and BP CML^{29*}

CHR**	WBC \leq institutional upper limit of normal (ULN) ANC \geq 1.0 x 10^9 /L Platelet count \geq 100 x 10^9 /L BM Blasts \leq 5% *** No peripheral blood blasts or promyelocytes; Peripheral blood myelocytes + metamyelocytes $<$ 5%; Basophils in peripheral blood $<$ 5%* No evidence of extramedullary involvement
-------	--

*The maximum % of basophils in peripheral blood was modified from < 2 to $< 5\%$ for a less restrictive constraint and alignment with the CHR criteria for CP CML patients according to ELN guidelines.

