Second, for the set of variables collected to derive peripheral blood or bone marrow differentials at each post-baseline visit up to week 13, if a given set are still incomplete, a non-missing set of lab variables obtained ± 3 days from the scheduled visit will be utilized to complete the derivation. For visits on or after week 13, a non-missing set of lab variables obtained ± 7 days of the visit will be utilized to complete that post-baseline assessment. The last non-missing peripheral blood or bone marrow differentials collected at week 1 day 1 or up to 30 days prior to week 1 day 1 will be used for baseline assessment. For example, if the bone marrow blast count was missing, the entire non-missing bone marrow assessment, not just the blast field, from another observation will be used. Some data handling rules for data combination are specified below.

- Data combination is needed only when the full dataset is not available on a single day at a given visit. The full dataset includes peripheral blood differential for chronic phase, and both bone marrow (when available) and peripheral blood differentials for advanced phase. The extramedullary assessment when absent should not preclude the derivation, and when present should be taken into account per response criteria rules.
- During the post-baseline data combination, the latest date will be used as the date of visit and the more conservative value will be taken if there is more than one measurement for a variable. For platelet counts, in case of multiple values, the lowest value will be taken. If any value falls above or below normal range, the out-of range value will be taken.

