**If an on-treatment CBC is scheduled within 1 week from the last platelet transfusion or last dose of G-CSF, it should be considered "Not Evaluable" for hematological response assessment, and a CBC should be repeated at least 1 week from the last platelet transfusion or last dose of G-CSF received.

***CHR for AP/BP that the 5% BM blasts is only required when a BM differential is available.

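### SAP Section 7 sets aside a missing spleen or extramedullary assessment even after a positive one, so a confirmed CHR can rest on blood counts alone

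*SAP*

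**What the plan says.** **Response criteria.** Protocol Appendix 11 and SAP Appendix 2 include "Spleen nonpalpable" among the CP criteria for CHR and "No evidence of extramedullary involvement" among those for AP/BP. Protocol Section 7.1.1.2 makes the examination part of the determination: besides blood counts, "extramedullary disease assessment (liver and spleen assessment) from the physical examination and bone marrow differentials will be used to determine response".

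**Missing data.** SAP Section 7 defines what must be present before a hematologic response is derived: "The full dataset includes peripheral blood differential for chronic phase, and both bone marrow (when available) and peripheral blood differentials for advanced phase". Spleen and extramedullary findings are not in that set. The next sentence begins: "The extramedullary assessment when absent should not preclude the derivation". It goes on to say that an assessment that is recorded is to be used under the response criteria. Nothing there distinguishes a patient whose previous assessment was clear from one whose previous assessment was positive. The opening of the same section rules out, in general, imputation such as carrying the last value forward. In AP/BP the marrow blast criterion is also conditional: it "is only required when a BM differential is available" (SAP Appendix 2).

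**Schedule.** For Weeks 1, 2, 3, 4 and 8, Protocol Section 6.2 lists "Extramedullary disease assessment, if clinically indicated". It adds that sites identified at screening should be followed, without fixing a visit. Protocol Table 1 and Section 6.2 place the first on-treatment physical examination at Week 13. Protocol Section 6 states in general terms that disease assessments take place at Weeks 1 to 4 and 8.

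**The concern.** For a patient with a clear spleen and no extramedullary disease at entry, waiving a missed examination is reasonable. For a patient with a positive finding at entry, the waiver removes the one criterion that patient has yet to meet. The error can only go towards response, because an absent assessment can never turn a true responder into a non-responder under this rule.

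At stake is chiefly the secondary endpoint of cumulative confirmed CHR in CP, AP and BP. A narrower part of the primary AP/BP endpoint is also involved, since OHR is CHR or RCP. The rule also sits oddly beside the SAP's other choices. When several values exist for one variable, Section 7 takes the more conservative one. Appendix 2 makes counts taken soon after a platelet transfusion or G-CSF not evaluable. Section 8.2.1 treats anyone who has not demonstrated a response as a non-responder.

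**Working it through.** The plan gives no figure on this point to reproduce. The check covers timing, consequence, endpoints and size.

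**1. Can a CHR be confirmed before any scheduled examination?** Visits on Day 7 of Week w fall on day 7 × w: Weeks 1, 2, 3, 4 and 8 are days 7, 14, 21, 28 and 56, and Week 13 is day 91. SAP Section 6.1 requires two consecutive responses at least 28 days apart.
- Week 4 to Week 8: 56 − 28 = 28 days (26 to 30 with the ±1 day windows, so some pairs fall short).
- Week 3 to Week 8: 56 − 21 = 35 days (33 to 37, always sufficient).
- Week 8 to Week 13: 91 − 56 = 35 days.

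So a CHR can be confirmed by day 56, which is 35 days before the first listed on-treatment physical examination.

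**2. What happens to a patient with a positive screening finding?** The extramedullary assessment is mandatory at screening. A CP patient with CHR-level counts and a palpable spleen is therefore not in CHR at baseline. With unchanged counts and no recorded examination at Weeks 4 and 8, the same patient is derived as a confirmed CHR, and SAP Section 6.1 counts it as an improvement from baseline.

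**3. Does Week 13 undo it?** No. Cumulative response is any on-treatment response (SAP Section 6.1). The extramedullary part of the loss-of-CHR definition (Protocol Section 5.3, SAP Section 6.1) covers only disease that was not there at baseline, so a persisting finding does not register as loss under that criterion.

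**4. Which endpoints are exposed?**
- *Cumulative confirmed CHR (secondary; CP, AP, BP):* exposed for both spleen and extramedullary disease.
- *OHR with splenic disease only:* SAP Appendix 1 exempts the spleen from the chronic-phase criterion on extramedullary blasts. An AP/BP patient with CHR-level counts (no peripheral blasts or promyelocytes, basophils below 5%, platelets at least 100 × 10⁹/L) but a palpable spleen meets the chronic-phase count criteria, and so counts through RCP in any case.
- *OHR with non-splenic extramedullary blasts:* these fail both CHR and RCP if recorded, and can pass if no assessment is recorded. Appendix 1 classes such patients as BP. The primary analysis reports AP and BP separately (SAP Section 8.2.1), so the exposure lies in BP and AP is largely unaffected.
- *MCyR:* unaffected.

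**5. Size.** A rate is inflated only by patients who meet every one of four conditions, so

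inflation = s × f × a × b,

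where s is the share with involvement at baseline, f the share of those whose counts meet CHR while the finding persists, a the share of those with no assessment recorded at the response visits, and b the share of those who never achieve a genuine confirmed response later. The documents give none of the four. With assumed values:
- low: 0.10 × 0.20 × 0.50 × 0.25 = 0.0025, or 0.25 points;
- high: 0.30 × 0.40 × 0.50 × 0.50 = 0.03, or 3 points.

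In small cohorts a single patient matters more than this range suggests: one misclassified patient moves the rate by 100/n points, which is 10 points for an assumed n of 10 and 5 points for an assumed n of 20.

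**The case against.** The strongest reply is that the protocol already looks after these patients. Sites found at screening are to be followed, and the Weeks 1 to 8 visit list itself repeats this. Disease assessments are stated for Weeks 1 to 4 and 8, liver and spleen findings are part of response determination, and the SAP uses any assessment that is recorded. On that view, a response on counts alone is a lapse and not the planned path. This stands as a reason to expect few cases. It does not close the gap, because no visit before Week 13 is fixed for the examination and the SAP does not make the response depend on one.

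A second reply is that the SAP never says a prior positive is to be disregarded. That is correct. The reading rests on an unqualified waiver together with the general exclusion of carry-forward. The text contains no exception that a programmer could apply.

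A third reply is that the remedy introduces a form of carry-forward and can err the other way, since a spleen that cleared by Week 4 but was first examined at Week 13 would be dated late. This is fair, and it is the reason to show the results under both rules.

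**Conclusion.** The point holds as a defect in a derivation rule, with limited reach. It affects secondary cumulative confirmed CHR in all three phases. It touches primary OHR essentially only for BP patients with non-splenic extramedullary blasts, a subset whose size the documents do not give and which may be empty.

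Two stronger readings are tempting. A reader might infer that every OHR in a patient with splenomegaly at entry is suspect. The documents do not support that, because the chronic-phase criteria exempt the spleen and such a patient reaches OHR through RCP. A reader might also take the inflation to be simply s × f, which for the same assumed values gives 0.10 × 0.20 = 2 points to 0.30 × 0.40 = 12 points. That ignores recorded assessments, which the SAP does use. It also ignores that the endpoints are cumulative (through Week 52 with a window to Week 56, or any time on treatment), so a patient whose finding clears later and whose counts hold is a genuine responder with only the date changed.

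The 0.25 to 3 point range is illustrative and rests wholly on assumed inputs. The study is descriptive, with no hypotheses or decision rules (SAP Section 4), so no formal conclusion turns on this. The correction is still worth making because the error goes one way and the remedy is cheap.

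**What to change.** In SAP Section 7, qualify the waiver along these lines: if the most recent spleen or extramedullary assessment, including baseline, was positive, a missing assessment does not count as satisfying the criterion. CHR (or RCP, where the finding is non-splenic extramedullary blasts) is then not derived until a recorded assessment shows resolution. If the most recent assessment was negative, the present rule stays.

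Report the present rule as a sensitivity analysis, and give the number of CHR and OHR responses derived without an assessment. Both results are worth showing because SAP Section 8.2.2 states that all patients had already passed Week 52, so this changes a derivation on data already collected.

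The cost is one sentence and a programming change; no new data are needed. Some response dates move to Week 13 or later. A patient who stops treatment before re-examination becomes a non-responder, so CHR rates, and possibly BP OHR, may fall slightly.
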